3.3. Estimands

3.3.1. Primary Estimand

The estimand for the primary objective is defined as follows:

- Treatment: 4 weeks follow up after 4 weeks of CC administration of rhNGF new formulation (CCI and vehicle).
- Population: Male and female patients aged ≥ 18 years with dry eye. Full Analysis Set.
- Variable: mean change from baseline to week 8 in symptoms of dry eye assessed by SANDE Global Score.
- Intercurrent events (ICEs) and strategies to handle them:
 - Treatment discontinuation (only IMP): a treatment policy strategy will be applied where all the observed values will be used regardless of the occurrence of the ICEs. Missing data due to any reason will be handled by using a multiple imputation with a copy-reference approach (see [Section 8.1.1](#) for further details).
 - Use of a prohibited medication, in the week before any assessment of SANDE Global Score: a hypothetical strategy will be applied where any data collected in the week after the occurrence of the ICE will be discarded. Missing data will be imputed by using a multiple imputation with copy-reference approach (see [Section 8.1.1](#) for further details).
- Population-level summary: difference in mean change from baseline to week 8 in

symptoms of dry eye assessed by SANDE Global Score between each concentration group of Investigational Medicinal Product (IMP - groups IMP1 and IMP2) and the vehicle group as derived by the Mixed Model for repeated measures defined in [Section 8.1.1](#).

In summary, the primary estimand is defined as the difference in mean change from baseline to week 8 in symptoms of dry eye assessed by SANDE Global Score between treatments in the targeted patient population regardless of study treatment discontinuation and had prohibited medications not been available to patients in the week before any study evaluation.

3.3.2. Key Secondary Estimands

Key secondary objective #1

The estimand for the key secondary objective #1 is defined as follows:

- Treatment: 4 weeks of CCI administration of rhNGF new formulation (CCI and vehicle).
- Population: Male and female patients aged ≥ 18 years with dry eye. Full Analysis Set.
- Variable: proportion of patients improving to Schirmer-I test without anesthesia ≥ 10 mm/5min in the Study Eye at week 4 (V4).
- ICEs and strategies to handle them:
 - Treatment discontinuation (only IMP): a treatment policy strategy will be applied where all the observed values will be used regardless of the occurrence of the ICEs. Missing data due to any reason will be handled by using a multiple imputation with a copy-reference approach (see [Section 8.2.1](#) for further details).
 - Use of a prohibited medication, in the week before any assessment of Schirmer-I score: a hypothetical strategy will be applied where any data collected in the week after the occurrence of the ICE will be discarded. Missing data for Schirmer-I score will be imputed by using a multiple imputation with copy-reference approach (see [Section 8.2.1](#) for further details), then the proportion of patients with an improvement ≥ 10 mm/5min in the Study Eye will be derived.
- Population-level summary: difference in proportion of patients improving to Schirmer-I test without anesthesia ≥ 10 mm/5min in the Study Eye at week 4 (V4) between each concentration group of IMP (groups IMP1 and IMP2) and the vehicle group as derived by a logistic model defined in [Section 8.2.1](#).

In summary, the estimand for the key secondary objective #1 is defined as the difference in proportion of patients improving to Schirmer-I test without anesthesia ≥ 10 mm/5min in the Study Eye at week 4 (V4) between treatments in the targeted patient population regardless of study treatment discontinuation and had prohibited medications not been available to patients in the week before any study evaluation.

Key secondary objective #2

The estimand for the key secondary objective #2 is defined as follows:

- Treatment: 4 weeks of CCI administration of rhNGF new formulation (CCI

- CCI and vehicle).
- Population: Male and female patients aged ≥ 18 years with dry eye. Full Analysis Set.
- Variable: mean change from baseline in Schirmer-I score without anesthesia in the Study Eye at week 4 (V4).
- ICEs and strategies to handle them:
 - Treatment discontinuation (only IMP): a treatment policy strategy will be applied where all the observed values will be used regardless of the occurrence of the ICEs. Missing data due to any reason will be handled by using a multiple imputation with a copy-reference approach (see [Section 8.2.1](#) for further details).
 - Use of a prohibited medication, in the week before any assessment of Schirmer-I score: a hypothetical strategy will be applied where any data collected in the week after the occurrence of the ICE will be discarded. Missing data will be imputed by using a multiple imputation with copy-reference approach (see [Section 8.2.1](#) for further details).
- Population-level summary: difference in mean change from baseline to week 4 in Schirmer-I score without anesthesia in the Study Eye between each concentration group of IMP (groups IMP1 and IMP2) and the vehicle group as derived by an ANCOVA model defined in [Section 8.2.1](#).

In summary, the estimand for the key secondary objective #2 is defined as the difference in mean change from baseline to week 4 in Schirmer-I score without anesthesia in the Study Eye between treatments in the targeted patient population regardless of study treatment discontinuation and had prohibited medications not been available to patients in the week before any study evaluation.

Key secondary objective #3

The estimand for the key secondary objective #3 is defined as follows:

- Treatment: 4 weeks of CCI administration of rhNGF new formulation (CCI and vehicle).
- Population: Male and female patients aged ≥ 18 years with dry eye. Full Analysis Set.
- Variable: mean change from baseline in total CCI in the Study Eye as assessed by the investigator at week 4 (V4).
- ICEs and strategies to handle them:
 - Treatment discontinuation (only IMP): a treatment policy strategy will be applied where all the observed values will be used regardless of the occurrence of the ICEs. Missing data due to any reason will be handled by using a multiple imputation with a copy-reference approach (see [Section 8.2.1](#) for further details).
 - Use of a prohibited medication, in the week before any assessment of CCI a hypothetical strategy will be applied where any data collected in the week after the occurrence of the ICE will be discarded. Missing data will be imputed by using a multiple imputation with copy-reference approach (see [Section 8.2.1](#) for further details).

- Population-level summary: difference in mean change from baseline to week 4 in total CCI in the Study Eye as assessed by the investigator between each concentration group of IMP (groups IMP1 and IMP2) and the vehicle group as derived by an ANCOVA model defined in [Section 8.2.1](#).

In summary, the estimand for the key secondary objective #3 is defined as the difference in mean change from baseline to week 4 in total CCI in the Study Eye as assessed by the investigator between treatments in the targeted patient population regardless of study treatment discontinuation and had prohibited medications not been available to patients in the week before any study evaluation.

3.4. Treatments

In the present document, the definition “study treatment” will always refer to the Investigational Medicinal Product (IMP) only (rhNGF or Vehicle).

3.4.1. Investigational Medicinal Product (IMP)

The IMP consists of:

- A sterile CCI containing vehicle or CCI mg/vial of rhNGF, packaged in a glass vial and administered after reconstitution with;
- CCI or 2mL of diluent contained into a separate glass vial.

CCI

CCI, the IMP is a sterile solution for ocular administration at the following concentrations as active ingredient:

- IMP 1: rhNGF C mcg/mL (C mL CCI)
- IMP 2: rhNGF C mcg/mL (C mL CCI)
- Vehicle IMP: rhNGF 0 mcg/mL (Vehicle in 1 mL or 2 mL diluent).

Details of IMPs are described in [Table 1](#).

Table 1. Description of Treatments			
Treatment Name	Vehicle IMP	IMP 1	IMP 2
Active Ingredient	none	rhNGF	rhNGF
Quality Control	Dompé Farmaceutici S.p.A. (Italy)		
Dose (daily)	CCI Vehicle	CCI	CCI mcg/mL/eye CC
Pharmaceutical form	CCI vehicle + CCI	CCI rhNGF + CCI	
Formulation	ophthalmic solution (CCI CCI)		
Regimen	CCI	CCI	CCI
Route of Administration	Ocular	Ocular	Ocular

Stability CCI of the CCI solution	CCI	CCI	CCI
Stability CCI of the pharmaceutical form	CCI	CCI	CCI

Investigational Medicinal Products will be dispensed to the patient as listed in the Schedule of Activities ([Appendix 13.1](#)).

3.4.2. Non Investigational Medicinal Product

The Non Investigational Medicinal Product (NIMP) will be used in the follow-up period only and will be dispensed at Visit 4 End of Treatment only. Details are shown in [Table 2](#) below.

Table 2. Description of NIMP	
Treatment Name during Follow-up Period	NIMP (preservative free artificial tears)
Dosage (daily)	CCI
Regimen	CCI, CC CCI
Formulation	Preservative free, sterile solution, single-use/multi-use
Route of administration	Topical ocular CCI

3.5. Dose Modification

Dose modification is not anticipated.

3.6. Definition of Study Eye

The Study Eye is the worst eye: assuming that all the inclusion/exclusion criteria are met in both eyes, the worst eye (Study Eye) will be determined at the baseline visit based on the lower Schirmer I (without anesthesia) score. If the Schirmer I score of both eyes is identical, the Study Eye will be determined based on the CCI. If both eyes are identical even considering NEI, then simply the right eye will be considered as the Study Eye.

4. General Statistical Considerations

Tabulations of summary statistics, graphical presentations, and statistical analyses will be performed with SAS® software, version 9.4 or higher.

Descriptive statistics for continuous variables in summary tables will include the number of patients in the analysis (n), mean, standard deviation (SD), median, first quartile (Q1), third quartile (Q3) and range (minimum, maximum). Descriptive statistics for qualitative variables in summary tables will include counts and percentages per category. If appropriate, 95% confidence intervals (CIs) around the mean or the proportion will be presented. The number of patients with missing data will be presented under the “Missing” category. Missing values will not be included in the denominator count when computing percentages. When continuous data are summarized, only the non-missing values will be evaluated for computing summary statistics. Any exception will be declared.

In general, regardless the strategy of the analysis described in [Section 8](#), a summary table with descriptive statistics will be produced for each efficacy endpoint. Summaries will be generated for observed cases, on absolute values and changes from baseline at each timepoint for continuous variables, on proportions at each timepoint for qualitative variables.

For the purpose of efficacy analyses in this trial, the statistical analysis (both descriptive and inferential) will be done on the Study Eye which is determined at baseline visit (visit 2). Details will be provided in the statistical analysis outputs as notes. In case the analysis involves both eyes, it will be clearly declared. This consideration only applies to the assessments that are done at individual eye level and does not apply to any assessment done at patient level (e.g., SANDE, CCI ...).

For summary precision, mean, median, Q1 and Q3 will have one more decimal place than the reported value, SD will have two more decimal places than the reported value, minimum and maximum will have the same decimal place as the reported value. Percentages and 95% CIs will have one decimal place. When count data are presented, the percentage will be suppressed when the count is zero in order to draw attention to the non-zero counts. A row denoted “Missing” will be included in count tabulations where specified on the shells to account for dropouts and missing values.

Data transformation (e.g. natural log transformation) might be used in order to satisfy the assumption of normality requested by parametric statistical tests and models. In case such assumptions are not met even on the transformed data, non-parametric counterpart tests will be used. In case the natural log transformation is used, a back transformation to the original scale will be also provided, in order to facilitate the clinical interpretation of the results.

All patient data collected on the eCRF will be listed by treatment group and patient and ordered by site, if applicable. If data is collected by eye, Study Eye will be flagged.

4.1. Sample Size

The sample size of the study is calculated based on results from the previous study

CCI
Expecting a mean difference of about 11 points (with unequal standard deviations in the active and vehicle groups: observed mean changes (SD) were -28.2 (26.36) and -17.4 (20.29) for IMP and vehicle, respectively) in improvement of SANDE Global Score from baseline to Week 8 in favor of rhNGF ophthalmic (CCI) formulation, a total sample size of 276 evaluable patients (92 per group) is needed. This will allow to achieve an overall power of CCI for demonstrating superiority of at least one concentration of rhNGF ophthalmic formulation over vehicle in the improvement of SANDE Global Score from baseline to week 8, with an overall one-sided alpha CCI .

CCI

Assuming a CCI of patients not evaluable for primary analysis after enrollment, the total number of patients to be enrolled in the study will be about 291 (97 per group).

In Dompé previous studies, a screen failure rate of about 20% has been observed. This implies that approximately 350 patients will need to be screened in order to have 291

patients enrolled and at least 276 evaluable. In any case, the screen procedures should be interrupted when the expected sample size of 291 patients has been reached.

4.2. Randomization, Stratification, and Masking

Interaction Response Technology (IRT) will be used to randomize the patients in a 1:1:1 ratio to each of the three treatment arms.

Eligible patients will be randomized in a 1:1:1 ratio to rhNGF **C** mcg/mL **CCl** (about 97 patients), rhNGF **C** mcg/mL **CCl** (about 97 patients) or vehicle ophthalmic solution **CC** (about 97 patients). Patients in the vehicle arm will be randomly assigned 1:1 to two different vehicle filling volumes to preserve masking. Nevertheless, all the patients randomized to the vehicle arm will be analyzed as a single treatment arm.

Each randomized patient will be allocated with a randomization number, according to the stratified randomization list. Dropouts after randomization will not be replaced.

Randomization will be stratified by site to ensure balanced assignment across treatment groups within each site. The stratified permuted block randomization list will be generated with a computer procedure by an independent statistician not involved in the conduct of the study.

This is a double-masked study. Appearance, including packaging and labeling, of the study products (IMP or vehicle) will not allow recognition of the actual treatment. Masked information on the identity of the assigned study products will be provided for each patient.

Unmasking can only occur in case of emergency, when knowledge of the treatment identity is essential for treating the patient. If the treatment code needs to be broken in the interest of patient safety for a medical emergency, the Investigator is allowed to break the treatment code for the specific patient, even before informing the Sponsor.

4.3. Analysis Set

The following analysis sets will be used in the statistical analyses.

4.3.1. Screened Population (SCR)

A patient will be defined as screened after the signature of the informed consent, the assignment of a Screening number and regardless of the completion of all the screening procedures. eCRF should be completed for each patient that signed the informed consent, including the screening failures.

4.3.2. Enrolled Population (ENR)

A patient in the SCR population will be defined as enrolled if meeting all the inclusion criteria and none of the exclusion criteria at the end of the screening procedure at Visit 1 (Day -12±2) and Visit 2 (Day 1). Patients in the SCR population but not included in the ENR population will be defined as screen failures.

4.3.3. Randomized Population (RND)

The Randomized population will consist of all patients in the SCR population who were assigned a randomization number.

4.3.4. Full Analysis Set (FAS)

The Full Analysis Set (FAS) will consist of all participants in the RND population who took at least one dose of IMP. The FAS will be analyzed according to the intention-to-treat principle, i.e. by treatment allocation. The FAS population will be used for the primary analysis of the study and to present results on efficacy data.

4.3.5. Per-Protocol Population (PP)

The Per Protocol (PP) population will consist of all patients in the FAS population who do not have major protocol deviations. Primary efficacy analysis will be conducted on the FAS population while SAF and PP populations will be used for safety and sensitivity analysis, respectively.

Reasons for the exclusion from the PP will be determined in the masked Data Review Meeting. A non-exhaustive list of possible reasons for exclusion from the PP can be found in [Section 5.2](#).

4.3.6. Safety Population (SAF)

The Safety (SAF) population will consist of all patients in the RND population who received at least one dose of the IMP. The Safety population will be analyzed according to the actual treatment received. The SAF population will be used to present results on safety data.

4.4. Analysis Window/Visit

For safety and efficacy endpoints, data will be evaluated and reported according to the nominal visit at which they have been collected, even if performed out of the tolerance interval limits declared in [Figure 1](#).

Efficacy analyses. Before applying any imputation methods, or any other strategy required by the handling of intercurrent events as detailed in [Section 3.3](#), a remapping will be done for any missing assessment at each planned visit. Remapping is allowed only for missing total scores (i.e. missing data for each item will not be replaced). In case data are missing at a given nominal visit, data collected at any other unscheduled visit (or ETV if done within an acceptable time-window of a previous visit) will be remapped to that visit, if the date of collection is within the tolerance interval limits defined in table of activities in [Section 13.1](#) (i.e. ± 1 for V3 – Day 13, ± 1 for V4 – Day 28, ± 2 for V5 – Day 56). Data collected under a nominal visit at out of tolerance interval limits will be used in the analysis unless the patient is declared an early study withdrawal: in this latter case, the evaluations recorded under the nominal visit will be set to missing and the actual values will be moved to a new timepoint named “Early Termination Visit”. This new timepoint will be only listed.

Safety analyses. Data collected under a nominal visit at out of tolerance interval limits will be treated as described for the efficacy. Data collected at an “Early Termination Visit” will be tabulated, separately from nominal visit values (i.e. Week 4 and Week 8).

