*In case of premature discontinuation of the study, the subject will be required to participate at the Early Exit Visit that will have the same assessment of Visit 4 (in case of early treatment discontinuation before Visit 4) or the same assessment of Visit 5 (in case the discontinuation from the study will occur after the ending of the treatment but before the expected Visit 5). A flag will be inserted in the eCRF to define if the Visit 4 or 5 is a per protocol visit or if it is done as Early Exit Visit.

** An ancillary kit will be also provided, see §6.3

[figure not shown]
^ CCI will be administered to all subjects but completed only by those that either have CCI or have filled this form before.

*** Only in patients with CCI

**** All ocular and systemic medications, over-the-counter painkillers, herbal products, vitamins, and antacids taken within 4 weeks prior to the start of and throughout the study will be clearly documented on the Concomitant Medications eCRF page.

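### SAP 4.4 sets an out-of-window Visit 4 to missing because the patient later withdraws, even when that visit was a genuine Week 4 examination and not the exit visit

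*SAP*

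**What the plan says.** SAP 4.4 opens with a general rule for safety and efficacy: "data will be evaluated and reported according to the nominal visit at which they have been collected, even if performed out of the tolerance interval". The tolerance for post-baseline efficacy visits is ± "1 for V4 – Day 28, ± 2 for V5 – Day 56", that is, Day 27-29 for Visit 4 and Day 54-58 for Visit 5.

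The efficacy paragraph then adds an exception. Out-of-window data under a nominal visit are used "unless the patient is declared an early study withdrawal: in this latter case, the evaluations recorded under the nominal visit will be set to missing". Such values go to a new timepoint called Early Termination Visit. For efficacy, "This new timepoint will be only listed". Safety values are moved in the same way but tabulated apart from Week 4 and Week 8.

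The remapping rule in the same section can fill a missing nominal visit from an unscheduled or early termination visit, but only if the date lies inside the tolerance interval.

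The protocol has sites record an exit examination as Visit 4 or Visit 5, and provides a marker to tell the two apart (Protocol 1.2, first footnote to the schedule): "A flag will be inserted in the eCRF to define if the Visit 4 or 5 is a per protocol visit or if it is" an early-exit examination. Protocol 4.1 and 8.2 and SAP Appendix 13.1 describe the same flag. SAP 4.4 does not refer to it.

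**The concern.** The exception has a sensible purpose. An exit examination on, say, Day 15 that is entered under Visit 4 should not count as Week 4. But the condition is on the patient, not on the visit. A patient can finish treatment, attend a true Visit 4 slightly outside the window, and leave the study some weeks later. Read as written, the rule reaches back and removes that Visit 4.

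Whether Week 4 data are analysed then depends on something that happens after Week 4. Two patients with identical Visit 4 dates and measurements are handled differently. This conflicts with the opening rule of 4.4, and the reason for the exception (the visit was not really Week 4) does not apply to a genuine Visit 4.

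Three key secondary endpoints sit at Week 4: Schirmer-I response, Schirmer-I change and corneal staining. The Week 4 SANDE also feeds the imputation of the primary Week 8 value.

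**Working it through.** **Applying the rule to Visit 4 dates.** Inputs: the window Day 27-29 and the exception, both from SAP 4.4.

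| Day of Visit 4 | Completer | Attends Visit 4, withdraws in follow-up |
|---|---|---|
| 28 or 29 | used | used |
| 30 (one day past the window) | used | set to missing |
| 26 (one day before it) | used | set to missing |

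Day 29 is one day after the target but inside the window, so it is kept. The problem starts at Day 30, or at Day 26 on the early side. Remapping cannot restore the value, because it accepts only in-window dates. If the same patient's exit Visit 5 is also out of window, the text sends both visits to one Early Termination Visit timepoint.

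**What happens to the removed values.**

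- *Key secondary endpoints (SAP 8.2.1).* The missing Week 4 Schirmer-I and staining values are filled by the copy-reference method, whose model is built from vehicle observations only (SAP 8.1.1). Observed data give way to imputed data.
- *Primary endpoint (SAP 8.1.1 and Appendix 13.3).* The imputation uses baseline, Week 4 and Week 8 SANDE. With Week 4 removed, only baseline is left to predict a missing Week 8 value. The MAR sensitivity analysis (SAP 8.1.2) also uses Week 4 and is affected in the same way.
- Week 8 will usually be missing for these patients, but not always: an exit examination falling on Day 54-58 would be kept as Week 8.

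**The plan's own figures.** The enrolment target reproduces. With a difference of 28.2 − 17.4 = 10.8, SDs of 26.36 and 20.29 (root mean square 23.52) and one-sided alpha 0.0125, a Welch t calculation gives 92 per group, with 80.2% power. Then 92 / 0.95 = 96.8, rounded up to 97 per group, and 3 × 97 = 291. None of this changes under the point made here; 291 and 5% are carried forward as inputs.

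**How many patients.** The documents give neither the share of withdrawals that come after Visit 4 nor the share of Visit 4 examinations outside the window. Both are assumed below.

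Formula: patients affected = 291 × (withdrawal rate) × (share withdrawing after Visit 4) × (share of Visit 4 out of window).

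- Withdrawal 5% (dropout rate in Protocol 6.4.2; non-evaluable rate in 10.1), low end: 291 × 0.05 × 0.25 × 0.10 = 0.36.
- Same withdrawal, high end: 291 × 0.05 × 0.75 × 0.30 = 3.27.
- Withdrawal 2%: 0.15 to 1.31.
- Withdrawal 10%, twice the planned rate: 0.73 to 6.55.

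At the planned rate this is about 0.4 to 3.3 patients across three arms, roughly one per arm at most.

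**The case against.** The strongest reply is that this is loose wording with an obvious intent. The destination is named Early Termination Visit, sites enter exit examinations under Visit 4 or 5, and the SAP reproduces the flag in its own schedule. A sensible programmer might apply the exception only to exit visits. The intent is probably as described. But the text does not say so, the SAP declares itself governing over the protocol, and its purpose is to fix such choices before unmasking. Followed literally, it discards valid data.

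A second reply is that the effect is small and probably conservative. That stands. Giving an active-arm patient vehicle-based Week 4 values credits no benefit to rhNGF. For the primary endpoint, a missing Week 8 is vehicle-imputed either way and only a predictor is lost. The complete-case and observed-case analyses already leave out patients with no Week 8 value. No inflation of false-positive risk is shown.

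A reader might infer two stronger points that the documents do not support.

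- *That the rule contradicts the estimand outright.* SAP 3.3.1 says "a treatment policy strategy will be applied where all the observed values will be used regardless of the occurrence of the ICEs", but as the strategy for discontinuing IMP. A patient who completed treatment and then left the study has had no such event. The conflict is real only for those who also stopped IMP early.
- *That the loss is differential because rhNGF causes eye pain.* The affected patients attended Visit 4 and left during follow-up, when they were on artificial tears. The documents place the pain during treatment, and ask patients who stop IMP for adverse events to stay for assessments (Protocol 7.1.1). Nothing ties pain to withdrawal after Visit 4.

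**Conclusion.** Wrong as written, low severity. SAP 4.4 lets a later withdrawal decide whether a genuine but out-of-window Visit 4 counts as Week 4. The removed values are not erased: efficacy values are still listed and safety values tabulated separately. They do leave the Week 4 efficacy analysis.

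The likely size is 0.4 to 3.3 patients in the whole trial. That rests on 5% withdrawal (the planned rate) and on two assumed ranges: 25-75% of withdrawals after Visit 4, and 10-30% of Visit 4 examinations out of window. Reaching six or so would need withdrawal at about twice the planned rate with both other assumptions at their upper ends. The expected direction in the active arms is conservative. The case for changing the rule is that it is internally inconsistent and cheap to correct; it is not expected to move the result.

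**What to change.** In SAP 4.4, tie the exception to the visit instead of the patient. Suggested wording: *Data recorded under Visit 4 or Visit 5 that the eCRF flags as an Early Exit Visit and that fall outside the tolerance interval are moved to Early Termination Visit. Data flagged as a per-protocol visit are analysed at the nominal visit whether or not the patient later withdraws.*

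The safety paragraph refers back to the efficacy rule, so it follows without separate editing. The handling of true exit visits is unchanged. The cost is one sentence and the matching program line, with no new data and no change to the sample size. It should be settled before unmasking; if that has passed, the handling actually used should be stated in the clinical study report.
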